4.2.6.3 Sensitivity analyses for the primary outcome variable

Sensitivity analyses may explore the effect of including other baseline covariates if imbalances in important factors are observed.

For the primary analyses of binary endpoints, participants who require any rescue therapy during the study will be classified as non-responders from the time of rescue use up until Week 16. Participants with missing data for binary endpoints will also be considered non-responders. Sensitivity analyses that may be performed to explore the impact of rescue therapy use and missing data on the results may include:

- Participants with rescue therapy use (from Day 29 onwards) remain as non-responders, other missing data at Week 16 will be imputed using LOCF approach;
- Treatment policy approach to handle rescue therapy use where all observed data is included in the analysis regardless of rescue therapy, missing data will be considered non-responders;
- All observed data will be included in the analysis regardless of rescue therapy, but with no imputation of missing data to be non-responders.

Additional sensitivity analyses for the primary and key secondary endpoints based on different missing data mechanism assumptions, may be used to explore the robustness of any treatment effect including multiple imputation approaches, if the amount of missing data warrants further investigation. Details of multiple imputation techniques for continuous endpoints are specified in Appendix 8.1, and can be adapted for binary endpoints if required.

4.2.7 Secondary outcome variables

4.2.7.1 Proportion of skin clearance EASI

The first and third key secondary endpoints of proportion of participants with skin clearance EASI-75 and EASI-90 at Week 16 for benralizumab 30 mg Q4W and placebo treatment groups will be analyzed using a logistic regression model in a similar way to that described for

the primary endpoint analyses (Section 4.2.6.1) including baseline EASI as a covariate instead of baseline IGA.

The observed proportion of responders will be summarized using descriptive statistics by treatment group and each scheduled visit.

For each of the first and third key secondary endpoints, the null hypothesis is: the proportion of participants on benralizumab 30 mg Q4W is equal to the proportion of participants on placebo. Whereas, the alternative hypothesis is: the proportion of participants on benralizumab 30mg Q4W is not equal to the proportion of participants on placebo. That is,

$$H_0: \text{Difference in proportions (benralizumab 30 mg Q4W – placebo)} = 0$$

$$H_1: \text{Difference in proportions (benralizumab 30 mg Q4W – placebo)} \neq 0$$

Sensitivity analyses for the key secondary endpoints may be considered if appropriate to explore the impact of rescue therapy use or missing data. Details are described above for the primary endpoint (Section 4.2.6.3).

The secondary endpoints of proportion of participants with skin clearance EASI-50 and EASI-100 at Week 16 will be analyzed using the same logistic regression model as the key secondary endpoint.

The proportion of participants with skin clearance EASI-75 at Week 52 will be analyzed with logistic regression model as described above, comparing effects on the Q4W and Q8W maintenance regimens.

4.2.7.2 Proportion with improvement in peak pruritus numeric rating scale

The second key secondary endpoint of proportion of participants with an improvement of ≥ 4 points in peak pruritus weekly score at Week 16 for benralizumab 30 mg Q4W and placebo treatment groups will be analyzed using a logistic regression model in a similar way to that described for the primary endpoint analyses (Section 4.2.6.1).

The observed proportion of responders will be summarized using descriptive statistics by treatment group and each scheduled visit.

For the second key secondary endpoint, the null hypothesis is: the proportion of participants on benralizumab 30 mg Q4W is equal to the proportion of participants on placebo. Whereas, the alternative hypothesis is: the proportion of participants on benralizumab 30mg Q4W is not equal to the proportion of participants on placebo. That is,

$$H_0: \text{Difference in proportions (benralizumab 30 mg Q4W – placebo)} = 0$$

H_1 : Difference in proportions (benralizumab 30 mg Q4W – placebo) $\neq 0$

Sensitivity analyses for the key secondary endpoint may be considered if appropriate to explore the impact of rescue therapy use or missing data, respectively. Details are described above for the primary endpoint (Section 4.2.6.3).

The proportion of participants with improvement of ≥ 4 in peak pruritus weekly score at Week 52 will be analyzed as described above, comparing effects on the Q4W and Q8W maintenance regimens.

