3 PRIMARY AND SECONDARY VARIABLES

3.1 General definitions

3.1.1 Baseline definition

Generally, for efficacy data, the last recorded value on or prior to the date of randomization will serve as the baseline measurement. If time is collected, the assessment performed the same day but at a time prior to randomization will be included in the baseline definition. This includes both, the Week 16 primary and the Week 52 final analyses.

Generally, for safety data, the last recorded value on or prior to the date of the first dose of IP will serve as the baseline measurement. If time is collected, the assessment performed the same day but at a time prior to the first dose of IP will be included in the baseline definition. This includes both, the Week 16 primary and the Week 52 final analyses.

For the Peak Pruritus Numeric Rating Scale (NRS), the average of the daily scores for the 7 days prior to the day of randomization will be the baseline. If there is no value prior to the date of randomization, then the baseline value will not be imputed and will be set to missing. Further details on scoring the Peak Pruritus NRS will be provided in Section 3.3.2.

For PROs with recall periods of 1 week or more (POEM, DLQI/CDLQI, HADS, PGI-S, CCI EQ-5D-5L, SF-36v2), the time component of the definition of baseline (ie time of assessment relative to randomization) will not be considered; assessments on the same

day as randomization will be used to calculate baseline. If there is no assessment prior to randomization (or on the same day), then the baseline value will not be imputed and will be set to missing. Further details on scoring for PROs will be provided in Section 3.3.

When time of assessment is not recorded or missing, it is assumed that assessments recorded on the date of first dose of IP were performed prior to dosing, except in cases of protocol specified post-dose assessments. If there is no value prior to randomization (or the first dose of IP, depending on the endpoint), then the baseline value will not be imputed and will be set to missing. No data known to be collected post first dose will be used in determining the baseline value, unless otherwise specified.

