3.1.5 Intercurrent Events

Intercurrent events are withdrawal from the study at any time or requiring rescue therapy from Day 29 onwards. However, participants who started on placebo and switched to benralizumab in the extension phase are additionally permitted rescue therapy for 28 days from starting benralizumab, and thus additionally any rescue therapy use from Day 141 (ie 29 days after first dose of benralizumab) onwards will be considered as intercurrent event for these participants.

Withdrawal from the study will be considered from the day after withdrawal onwards, thus data on the day of withdrawal will be used as recorded. Rescue therapy from Day 29 (of first dose, and additionally for placebo-benralizumab participants from first benralizumab dose) onwards will be considered for intercurrent event imputation from the day of taking rescue medication onwards.

For responder or binary analyses, participants with intercurrent events will be considered as non-responders from the time these events occur. Participants with missing data for binary endpoints will also be considered non-responders at affected post baseline visits. Intercurrent events will be considered for analyses and descriptive summaries.

For change from baseline analyses or number and percentage of score category summaries, participants with intercurrent events will be considered as having missing scores from the time these events occur. Intercurrent events will be considered for analyses and descriptive summaries.

For summaries of number and percentage of individual questionnaire scores, all data will be presented as recorded, without imputation for intercurrent events.

The categorisation and imputations of responder status and reasons for non-response are provided in following table.

Table 3 Response Category Imputations

Response Category	Imputation Rule
Responder	Keep data as recorded, unless after taking rescue medication
Non responder	
Recorded as non-responder	Keep data as recorded, even if after taking rescue medication

Table 3 Response Category Imputations

Response Category	Imputation Rule
Missing	For missing questionnaire/visit, where participant remains in study and could be Responder or Recorded Non-responder or Rescue medication and remain in study
Rescue medication and remain in study	Impute if recorded as Responder and participant ongoing in study. Impute from day of rescue medication onwards, but only for assessments where participant is a Recorded Responder

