3.3.2 Peak Pruritus Numeric Rating Scale

The proportion of participants with an improvement of ≥ 4 points in peak pruritus weekly score at Week 16 will be used as the second key secondary efficacy variable.

The Peak Pruritus NRS is a one-item daily assessment of the worst itch the participant experienced over the past 24 hours. This is recorded every evening from Visit 1 onwards on the electronic device supplied to the participants. The score ranges from 0 to 10, with 0 being “no itch” and 10 being “worst itch imaginable.” and so a reduction in score is considered an improvement.

If a participant has at least 4 non-missing daily scores in a 7-day week, the peak pruritus weekly score is defined as the sum of the available daily scores divided by the number of days with non-missing daily scores. If there are less than 4 non-missing daily scores, then the weekly score is missing for that week.

The second key secondary endpoint is a binary response that will classify a participant as a responder if there is an improvement of 4 or more points in peak pruritus weekly score at Week 16 relative to baseline. Otherwise, participants will be classified as a non-responder.

In the statistical analyses, a binary variable will take on value 1 if a participant is defined as a responder, and value 0 for non-responder, and will be used as the response variable for the efficacy analysis.

The change from baseline in peak pruritus score at Week 2 will be analyzed as a secondary endpoint.

Intercurrent events will be considered as described above in Section Intercurrent Events (Section 3.1.5). Participants with a missing baseline score will have missing change from baseline status. Intercurrent events will be considered for analyses and descriptive summaries.

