4.2.6 Primary outcome variable

4.2.6.1 Primary analysis

The primary endpoint is the proportion of participants with IGA 0/1 (ie, clear or almost clear) and a decrease in IGA of 2 or more points at Week 16, relative to baseline. The null hypothesis is: the proportion of participants on benralizumab 30 mg Q4W is equal to the proportion of participants on placebo. Whereas, the alternative hypothesis is: the proportion of participants on benralizumab 30 mg Q4W is not equal to the proportion of participants on placebo. That is,

H_0 : Difference in proportions (benralizumab 30 mg Q4W – placebo) = 0

H_1 : Difference in proportions (benralizumab 30 mg Q4W – placebo) \neq 0

Hypothesis testing for the primary analyses will be performed according to the multiple testing procedure described in Section 4.1.1.

For the primary and key secondary endpoints, the primary estimand will be based on the FAS (Section 2.2.2). Intercurrent events will consist of participants who withdraw from the study or require rescue therapy (defined in CSP Section 6.5.3). The primary estimand will regard these participants as non-responders from the time such events occur up to Week 16. A participant with missing data at a specific time point will also be considered as a non-responder at that time point.

The primary endpoint is a binary response that classifies a participant's skin clearance at Week 16 using the IGA score (see Section 3.2). Participants will be classified as responders if IGA 0/1 (ie, clear or almost clear) and they have a decrease in IGA of 2 or more points relative to baseline. Otherwise, participants will be classified as non-responders.

For the primary analysis, a logistic regression model will be fitted to the primary endpoint using a logit link function. The model will include treatment group and baseline covariates for age at screening (≥ 12 to < 18 years/ ≥ 18 years), blood eosinophils at screening (< 300 cells/ μ L; ≥ 300 cells/ μ L), and baseline IGA score. The strata variables will be used as recorded in the database, however for missing eosinophil data from the central laboratory the IVRS results will be used.

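### The key secondary pruritus responder model, as written, adjusts for baseline IGA and not for baseline itch: a valid test that may give up some power

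*SAP*

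**What the plan says.** - **Section 4.2.6.1** fits a logistic regression with treatment, age stratum, eosinophil stratum "and baseline IGA score. The strata variables will be used as recorded in the database".
- **Section 4.2.7.1** takes the same model for EASI-75 and EASI-90, "including baseline EASI as a covariate instead of baseline IGA".
- **Section 4.2.7.2** takes it for the pruritus responder endpoint, where the "treatment groups will be analyzed using a logistic regression model in a similar way to that described for the primary endpoint analyses (Section 4.2.6.1"), and names no other covariate. It applies the same description to the Week 52 comparison of the Q4W and Q8W regimens.
- **Section 3.3.2** defines response as an "improvement of 4 or more points in peak pruritus weekly score at Week 16 relative to baseline".
- **Section 3.1.1** already derives the baseline: "the average of the daily scores for the 7 days prior to the day of randomization will be the baseline". If there is none, "then the baseline value will not be imputed and will be set to missing".
- **Section 3.1.5**: "Participants with missing data for binary endpoints will also be considered non-responders at affected post baseline visits".
- **Section 4.1.1** places this endpoint third of four in the fixed sequence, ahead of EASI-90.

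**The concern.** Adjacent sections use one cross-reference. One states a covariate swap and the other does not, so the natural reading of Section 4.2.7.2 is that baseline IGA stays. A fall of at least 4 points on a 0 to 10 scale depends on where the participant starts; someone with a baseline below 4 cannot respond at all. Leaving that baseline out may discard precision that costs nothing to collect.

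Two things are at stake. One is power for an alpha-controlled test that also gates EASI-90. The other is specification. Table 11 gives the odds ratio as the summary measure, and a covariate-adjusted odds ratio changes with the covariate set. An unclear covariate therefore leaves unclear which odds ratio is reported. The standardized risk difference does not have that problem.

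**Working it through.** **1. The plan's own power figures.** Section 1.2 assumes 40% versus 10% for the primary endpoint, two-sided 5%. With power = Φ{[d − 1.96·√(2p̄(1−p̄)/n)] / √[(p₁(1−p₁)+p₂(1−p₂))/n]}, d = 0.30 and p̄ = 0.25:

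- n = 80: (0.300 − 1.96 × 0.0685)/0.0642 = 2.58, power 99.5% (plan: above 95%).
- n = 35: (0.300 − 1.96 × 0.1035)/0.0971 = 1.00, power 84.1% (plan: at least 80%).

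Both reproduce. No power figure is given for pruritus.

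**2. Why the baseline matters, and when it does not.** Suppose Week 16 score = a + b × baseline + error. The fall is then (1 − b) × baseline − a − error. Take a baseline SD of 1.8 and a residual SD of 2.2 (assumed). One SD of baseline shifts the fall by (1 − b) × 1.8/2.2 residual SDs: 0.57 at b = 0.3, 0.41 at b = 0.5, 0.16 at b = 0.8 and 0 at b = 1.0. Any gain should therefore shrink to nil as b approaches 1.

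**3. Simulation A.** Inputs: 80 per arm (SAP Section 1.2). Assumed, not in the SAP: baseline mean 7.2, SD 1.8, residual SD 2.2, IGA–pruritus correlation 0.3, slope b from 0.3 to 1.0, and the response rates. Model: logit P(response) = β₀ + β₁·treatment + β₂·age + β₃·eosinophils + β₄·X, with X either baseline IGA or baseline pruritus. The test is Wald on β₁, and the SE of the standardized risk difference is by the delta method. 3000 trials per scenario. Power (%) with IGA → with baseline pruritus:

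| Rates | b = 0.3 | b = 0.5 | b = 0.8 | b = 1.0 |
|---|---|---|---|---|
| 28 vs 14 | 58.4 → 63.6 | 58.1 → 60.9 | 58.9 → 59.3 | 57.5 → 57.2 |
| 25 vs 10 | 70.3 → 74.7 | 70.1 → 73.2 | 70.3 → 70.7 | 70.4 → 70.4 |
| 35 vs 15 | 82.8 → 88.1 | 83.0 → 85.4 | 83.2 → 83.8 | 83.4 → 83.2 |

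At 40 vs 10 both models exceed 99% (99.4–99.6 → 99.5–99.8). Across all four rate pairs the SE changes by −5.6 to −6.9% at b = 0.3, −3.2 to −4.2% at 0.5, −0.7 to −1.1% at 0.8, and −0.1 to 0% at 1.0. The Monte Carlo error of one power estimate near 60% is √(0.6 × 0.4/3000) = 0.9 points, so the small falls at b = 1.0 are noise. A separate rerun on the same assumptions gave 59.2 → 64.5 (28 vs 14) and 84.2 → 87.9 (35 vs 15) at b = 0.3.

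**4. Simulation B, a different data model.** Baseline pruritus acts through an odds ratio per SD. The strata probabilities are 50/160 adolescent and 100/160 high eosinophil (SAP Table 2). At 27% versus 10%:

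| Odds ratio per SD | With IGA | With baseline pruritus |
|---|---|---|
| 1.0 | 78.6 | 78.8 |
| 1.5 | 80.1 | 80.8 |
| 2.0 | 80.4 | 82.9 |
| 3.0 | 80.0 | 85.8 |

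At 40% versus 10% both models give at least 99.4%.

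**5. Type I error.** Simulation A (6000 trials; slopes 0.3 and 0.8): 4.3% and 4.6% with IGA, 4.8% and 4.6% with pruritus. Simulation B (20% in both arms): 4.7 to 5.6% with either.

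**6. Missing baseline pruritus.** Assume 5% missing (0.05 × 160 = 8 participants), counted as non-responders, b = 0.5, 28 vs 14 before missingness, 4000 trials. The risk difference should be about 0.14 × 0.95 = 0.133.

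| Model | Participants | Risk difference | SE |
|---|---|---|---|
| IGA | 160 | 0.132 | 0.0620 |
| Pruritus, no fill-in | about 152 | 0.139 | – |
| Pruritus, overall mean filled in | 160 | 0.132 | 0.0597 |

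A bare swap loses participants and moves the estimate. The fill-in keeps both and lowers the SE by (0.0620 − 0.0597)/0.0620 = 3.7%.

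**The case against.** The SAP often cross-refers without renaming the baseline. Sections 4.2.7.4 to 4.2.7.8, 4.2.9.2 and 4.2.9.7 all point to the EASI repeated-measures model, which names baseline EASI, and none states a swap. Nobody would take these to mean that DLQI change is adjusted for baseline EASI only. By that habit, own-baseline adjustment may be implied in Section 4.2.7.2 as well, and then no precision is lost. This stands as a possible reading. It does not settle the matter, because the section immediately before uses the same cross-reference and found the swap worth stating. Nor is IGA an odd covariate that a programmer would notice and query.

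The size is also hypothetical. All pruritus inputs are assumed, and the gain is near nil for slopes of 0.8 and above. The power figures are not conditional on having passed IGA response and EASI-75; if the endpoints are correlated, trials that reach this test may have more power and less to gain. That was not computed. All of this stands.

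Baseline IGA also avoids the missing-diary problem shown in step 6. True, but one sentence deals with it.

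Finally, Section 4 keeps analysis staff blinded until the primary database lock, so a Week 16 covariate settled in programming before then is settled blind. That limits the concern about an open choice. It does not extend to the Week 52 model if that is settled after the primary lock.

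**Conclusion.** The point holds in its limited form. Followed as written, the pruritus responder test adjusts for baseline IGA and omits a baseline that the SAP already derives. The test is valid and randomization protects the comparison under either covariate. The possible loss is 0 to about 5 power points in simulation A and up to about 6 in simulation B at its strongest assumed association. It is immaterial if response rates resemble the 40% and 10% planned for the primary endpoint. These figures rest on assumed pruritus inputs and concern Week 16 only; the Week 52 comparison was not simulated. A change is recommended because the test is alpha-controlled and the remedy is short. The trial does not depend on it.

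**What to change.** In Section 4.2.7.2, for the Week 16 and Week 52 analyses, add text such as:

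> The model replaces baseline IGA with the baseline peak pruritus weekly score (continuous, Section 3.1.1). Participants without a baseline score stay in the full analysis set as non-responders; for the model covariate only, the overall mean baseline score across treatment groups is used, as an exception to Section 3.1.1. The baseline used to derive the endpoint is not imputed.

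The cost is this short addition, including one stated exception to the no-imputation rule. No new data are needed. The exception has a precedent in kind: Section 4.2.6.1 already substitutes the IVRS value when the central-laboratory eosinophil result is missing. If the sponsor prefers to keep baseline IGA, Section 4.2.7.2 should say so explicitly before unblinding.

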4.2.7.3 Change from baseline in EASI score

The secondary endpoint of change from baseline in EASI score will be analyzed by a MMRM model at Week 16.

The model will include change from baseline in EASI score as the dependent variable (derived for each participant and every scheduled visit up to Week 16); baseline EASI score as a continuous covariate; treatment, age at screening (≥ 12 to < 18 years/ ≥ 18 years), blood eosinophils at screening (< 300 cells/ μ L; ≥ 300 cells/ μ L), and visit as categorical factors; and treatment-by-visit as an interaction term. The strata variables will be used as recorded on the database. An unstructured variance-covariance matrix will be used to model within-subject errors, and the Kenward-Roger approximation will be used to estimate denominator degrees of freedom and to adjust standard errors, the OBSMARGINS option will be used to derive the LSMEAN estimates assuming mean values for the baseline covariates. If the model fails to converge, alternative variance-covariance models will be tried in the following order: Toeplitz, first-order regressive, compound symmetry.

For each visit, the model will be used to estimate the mean change from baseline for each treatment group (benralizumab 30mg Q4W and placebo) and difference between treatment groups, with corresponding 95% CIs and the p-value, corresponding to a 2-sided test.

The distributional assumptions of the MMRM model will be checked by examining plots of residuals. If the residuals suggest that it is unreasonable to assume that data follow a Normal distribution (eg, data are skewed and the constant variance assumption is not met), alternative models will be explored. For example, data may be log transformed prior to fitting the model, or a non-parametric method may be deemed more appropriate.

The observed means and mean changes from baseline will be summarized using descriptive statistics by treatment group and each scheduled visit up to Week 16.

Additional sensitivity analyses based on different missing data mechanism assumptions may be used to explore the robustness of any treatment effect, including

- Participants with rescue therapy use (from Day 29 onwards) will be imputed using LOCF approach and analyzed with analysis of covariance (ANCOVA);
- Treatment policy approach where all available data is included regardless of rescue use, and analyzed with MMRM;
- Multiple imputation techniques if the amount of missing data due to intercurrent events warrants further investigation.

Details of multiple imputation techniques for continuous endpoints are specified in Appendix 8.1.

Changes from baseline in EASI total score at Week 52 will be analyzed with MMRM model as described above, comparing effects on the Q4W and Q8W maintenance regimens.

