4.2.7.4 Change from baseline in peak pruritus numeric rating scale

The change from baseline in peak pruritus score will be analyzed using a MMRM model as described above for the change in EASI (Section 4.2.7.3). The change at Week 2 along with other supportive timepoints will be estimated from this model.

Descriptive summary statistics for scores and changes from baseline will be produced by treatment group and visit.

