4.2.7.5 Change from baseline in POEM score

The change from baseline in POEM score at Week 16 and at Week 52 will be analyzed using MMRM model as described for the change in EASI (Section 4.2.7.3).

Descriptive summary statistics for scores and changes from baseline will be produced by treatment group and visit.

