4.2.7.6 Change from baseline in SCORAD Index

The change from baseline in SCORAD Index at Week 16 and at Week 52 will be analyzed using MMRM model as described for the change in EASI (Section 4.2.7.3).

Descriptive summary statistics for scores and changes from baseline will be produced by treatment group and visit.

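### The MMRM in SAP 4.2.7.3 fits one baseline slope for all visits; a baseline-by-visit term would cost almost nothing and could sharpen the Week 16 estimates and make them more robust

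*SAP*

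**What the plan says.** SAP 4.2.7.3 specifies "baseline EASI score as a continuous covariate", with treatment, the age stratum, the eosinophil stratum "and visit as categorical factors; and treatment-by-visit as an interaction term". Treatment-by-visit is the only interaction. The residual covariance is left free: "An unstructured variance-covariance matrix will be used to model within-subject errors", with Kenward-Roger. Results are read off visit by visit: "For each visit, the model will be used to estimate the mean change from baseline for each treatment group".

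The model is then carried elsewhere by reference:
- EASI at Week 52 (4.2.7.3): "Changes from baseline in EASI total score at Week 52 will be analyzed with MMRM model as described above".
- Itch (4.2.7.4): the change "will be analyzed using a MMRM model as described above for the change in EASI".
- POEM (4.2.7.5): "The change from baseline in POEM score at Week 16 and at Week 52 will be analyzed using MMRM model".
- SCORAD (4.2.7.6): "The change from baseline in SCORAD Index at Week 16 and at Week 52 will be analyzed using MMRM model".
- DLQI (4.2.7.7), CDLQI (4.2.7.8), HADS (4.2.9.2) and BSA (4.2.9.7), in the same way.

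Table 1 names Week 16 as the time point for change in EASI, POEM, SCORAD and DLQI/CDLQI. For itch, the named continuous endpoint is Week 2. No section of the SAP adds a baseline-by-visit term.

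**The concern.** With baseline as a main effect only, one slope must serve every visit. A change score need not behave that way. If improvement is roughly proportional to baseline and builds up over time, the slope is shallow early and steep later. The fitted common slope is then a compromise, Week 16 is under-adjusted, and the misfit goes into the Week 16 residual variance. The precision lost comes from a value that every analysed participant should already have.

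A second route runs through missing data. SAP 4.1 sets values after rescue (from Day 29) or after withdrawal to missing, and 8.1.3 relies on a likelihood analysis under MAR. That protection needs a correct mean model. If the slope is wrong at Week 16, and the participants with missing data differ in severity and between arms, the error no longer cancels in the treatment difference.

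At stake are the precision, and to a lesser extent the accuracy, of the continuous secondary estimates at Week 16 and of the Week 52 comparison of regimens, which has a planned 40 participants per benralizumab sequence.

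**Working it through.** **The plan's own figure.** The SAP gives no SD, visit correlation, missing-data rate or power for any MMRM endpoint. Its only directly relevant planning figure is power above 95% for the binary primary endpoint (80 per arm, 40% v 10%, two-sided 5%). Check: null SE = sqrt(2 × 0.25 × 0.75/80) = 0.0685; alternative SE = sqrt((0.24 + 0.09)/80) = 0.0642; (0.30 − 1.96 × 0.0685)/0.0642 = 2.58, so power is 99.5%. The figure reproduces and does not depend on this point.

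**Formula.** Let b be the true slopes of change on baseline by visit, S the residual covariance and SD_B the baseline SD. In large samples the common slope tends to g = (1'S⁻¹b)/(1'S⁻¹1). The ratio of the Week 16 SE under a common slope to that under visit-specific slopes is sqrt(1 + (b16 − g)² SD_B²/σ16²).

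**Assumed inputs (none is in the SAP).** Four visits at Weeks 4, 8, 12 and 16; baseline EASI SD 11; residual SD either constant at 9 or rising 7, 8, 9, 10; visit correlation 0.6 to 0.8, autoregressive or exchangeable; slopes changing linearly from −0.35 to −0.50 (mild), −0.25 to −0.55 (moderate) or −0.20 to −0.65 (strong).

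**Constant SD.** By symmetry g is the mean slope.
- Mild: (0.075 × 11/9)² = 0.0084; ratio 1.004.
- Moderate: (0.15 × 11/9)² = 0.0336; ratio 1.017.
- Strong: (0.225 × 11/9)² = 0.0756; ratio 1.037.

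**Rising SD.** The common slope is pulled towards the early visits, and under high exchangeable correlation it falls outside the range of the true slopes.
- Moderate, autoregressive 0.8: g = −0.303; (0.247 × 11/10)² = 0.074; ratio 1.036.
- Moderate, exchangeable 0.8: g = −0.190; (0.360 × 11/10)² = 0.157; ratio 1.075.

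| Slope change | Week 16 SE inflation over all patterns |
|---|---|
| none | 0% |
| mild | 0.4% to 2% |
| moderate | 2% to 7.5% |
| strong | 4% to 16% |

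**Simulation check.** 400 trials per scenario, 80 per arm, four visits, unstructured maximum likelihood, without Kenward-Roger or the strata. Scenarios are defined by the assumed correlation of baseline with the Week 4 to Week 16 scores.

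| Correlation with baseline | Model-SE ratio, complete data | Model-SE ratio, about 21% dropout |
|---|---|---|
| constant 0.5 | 1.000 | 1.000 |
| 0.7 falling to 0.4 | 1.029 | 1.042 |
| 0.8 falling to 0.2 | 1.202 | 1.210 |

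The ratios of the empirical SDs of the estimates were 1.00, 1.03 and 1.19 on complete data, and 1.00, 1.01 and 1.15 with dropout. Dropout here followed severity with no separate arm effect, and the two models' mean estimates stayed within about 0.01 baseline SD of each other.

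**Missingness that also differs by arm.** Assume severity-dependent loss of about 32% on placebo and 13% on benralizumab by Week 16, and a true difference of −3.0 EASI points. In large samples the common-slope model gave −3.1 (mild), −3.25 (moderate) and −3.4 (strong), overstating benefit by 0.1/3 = 3% to 0.4/3 = 13%. With baseline-by-visit the estimates were −2.96 to −3.02. With equal slopes both models gave −3.0.

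**Itch.** With 16 weekly scores, variance inflation was under 3% at Week 2 (under about 1.5% in SE) and 5% to 7% at Week 16.

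Nothing was calculated for Week 52.

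**The case against.** The plan's model is a recognised one and valid for a randomised comparison. With complete data, a misspecified baseline slope costs precision without biasing the treatment difference. Nothing in the SAP is contradictory, and the SAP holds no data showing that slopes differ between visits. A reader might infer that Week 16 standard errors are in fact too large. The documents do not support that: the loss is zero if slopes are equal, and every non-zero figure here rests on assumed slopes, SDs and correlations. Much of the upper range also needs the residual SD to grow over time; at constant SD, mild to moderate change costs only 0.4% to 1.7%.

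A reader might also extend the point to itch at Week 16. The named continuous itch endpoint is Week 2, and later times are supportive. Nor does the point reach the trial's main conclusion. The hierarchy in 4.1.1 contains four binary endpoints analysed by logistic regression, 4.1 calls p-values nominal, and the sample size rests on the primary endpoint.

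Finally, the added parameters are not negligible everywhere. CDLQI is completed only by those aged 16 or younger, a subset of the 50 adolescents planned in Table 2.

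All of this stands. It limits the point to a conditional and optional one, but it gives no reason to keep the constraint. When slopes are equal, the extra term left the standard error unchanged.

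**Conclusion.** The point holds as a conditional recommendation. The model imposes a common baseline slope. If slopes change mildly to moderately across visits, the Week 16 SE is larger by about 0.4% to 7.5%; if they do not change, by 0%. Inflation of 16% to 20% appears only under strong slope change or strong decay of the baseline correlation and should not be taken as the expected size. If missingness after rescue or withdrawal depends on severity and differs by arm, the Week 16 EASI difference may shift by a few tenths of a point (0.1 to 0.4 on an assumed −3.0). That shift depends on assumed missing-data rates, since the SAP gives none. The primary result and the type I error of the hierarchy are untouched, and the effect on Week 2 itch is expected to be small. Severity: optional; a free improvement.

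**What to change.** In SAP 4.2.7.3, add a baseline score-by-visit interaction to the fixed effects, keeping the baseline main effect. State that it applies, with each endpoint's own baseline score, to every model that cites this section, including the Week 52 models.

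For CDLQI only, pre-specify that the baseline main effect alone may be kept if the model does not converge. Say where this step falls relative to the covariance fallbacks already listed (Toeplitz, first-order autoregressive, compound symmetry).

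The cost is one line in the SAP, one model term in the programs and (visits − 1) extra fixed-effect parameters: 3 if there are four visits to Week 16, and 15 for 16 weekly itch scores. No extra data are needed.
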